#### **Exclusion Criteria:**

- 1 Coagulopathies
- 2 Patients with continuous epidural
- 3 Uncooperative patient
- 4 Psychiatric disorders and language deficiencies that may interfere with the assessment of pain
- 5 Insufficient understanding of the pain scoring system.
- 6 Outpatient stay

This study will be performed at the John D. Dingell VA Medical Center. Only a trained MD anesthesiologist will recruit patient in the preoperative period, where informed consent will be obtained. Computerized randomization will take place at the time the patient presents for surgery. Consent will be taken preoperatively.

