# **STUDY DESIGN AND METHODS**

2

This will be a prospective randomized study to compare auricular battlefield acupuncture to sham auricular battlefield acupuncture in patients undergoing general surgery and urology cases with general anesthesia. Participants in the study will be randomly assigned to either receive auricular battlefield acupuncture (treatment group) or simulated (placebo; control group) auricular battlefield acupuncture. Battlefield acupuncture needles will be utilized in the test arm and blunt needle pressing and covering with acupuncture stickers will be utilized in the control arm as a sham treatment. Location of needles and stickers will be placed according to 5 VA approved BFA auricular acupuncture points associated with PONV, pain, and anxiety respectively (Figure 1; 3). In both arms, the treatment ear will be covered after treatment so as to blind the patient. Both battlefield acupuncture and control groups will receive small band aids on the battlefield acupuncture needle sites. Both the evaluators for post procedure assessment along with the patient will be blinded in regards to what group they are in.

Figure 1. Battlefield acupuncture points.

Source: Teresa M. Kerge et al 2013.US Service Members With Polytrauma. Practical Pain Managementhttp://www.practicalpainmanagement.c om/pain/spine/trauma/us-servicemembers-polytrauma

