#### **Anesthetic Plan:**

The anesthetic management will be general anesthesia with the provision of intravenous opioids intraoperatively and during recovery. Fentanyl will be the sole intra operative opioid. No other alterations of anesthetic management will take place pre or intra operatively. The battlefield acupuncture or sham battlefield acupuncture will be placed in the postoperative care unit (PACU).

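### The allocation is drawn when the patient presents for surgery although the arms first differ in the PACU; drawing it just before placement would be a cheap, small improvement

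*Combined protocol and SAP*

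**What the plan says.** All references are to the combined protocol and SAP.

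- **Consent and draw** (paragraph after the list under Exclusion Criteria). "Only a trained MD anesthesiologist will recruit patient in the preoperative period, where informed consent will be obtained". Then: "Computerized randomization will take place at the time the patient presents for surgery".
- **Treatment** (Anesthetic Plan). "The battlefield acupuncture or sham battlefield acupuncture will be placed in the postoperative care unit (PACU"). Before that, the arms are managed alike: "No other alterations of anesthetic management will take place pre or intra operatively". Techniques describes the treatment as postoperative in both groups.
- **Population.** Study Design and Methods describes "patients undergoing general surgery and urology cases with general anesthesia", and the Anesthetic Plan agrees: "The anesthetic management will be general anesthesia". The exclusions include "Patients with continuous epidural" and an outpatient stay; inclusion criterion 4 requires an inpatient stay.
- **Blinding** (Study Design and Methods). "Both the evaluators for post procedure assessment along with the patient will be blinded in regards to what group they are in". The intraoperative team is not mentioned.
- **Outcomes** (Data). Assessments are at 1 hour and 24 hours post procedure, with the later one at the bedside. None is listed before placement.
- **Sample size** (Statistical Analysis). 72 participants, 36 per group, for 80% power. There is no loss allowance, replacement rule or analysis population, and no rule for a patient who is randomised but never treated.

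**The concern.** The whole operation lies between the draw and the first moment at which the arms differ. In that interval a case may be cancelled, a continuous epidural may be placed, or the stay may become outpatient. Each such patient has already been randomised but is ineligible or untreated, and the plan does not say what the analysis does with them. The analyst would have to choose later between dropping and keeping them.

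The second issue is knowledge of the arm. The allocation exists during surgery, and the blinding statement covers only the patient and the post-procedure evaluators. A draw made after surgery would make it impossible for anyone to know the arm while intraoperative fentanyl is being given.

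**Working it through.** **1. Does any step before placement need the allocation?** Consent is preoperative and common to both arms. Anaesthetic management is the same in both. Treatment is postoperative in both. The first outcome comes after placement. So nothing before the PACU uses the allocation, and the documents give no reason for the earlier draw.

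**2. The plan's own figure.** The power statement gives no control rate and does not say whether the 33% reduction is absolute or relative, so 36 per group cannot be uniquely reproduced. With the pooled two-proportion formula (two-sided 0.05, 80% power)

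n = [1.96·√(2p̄(1−p̄)) + 0.842·√(p₁(1−p₁) + p₂(1−p₂))]² / (p₁−p₂)²,

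an assumed 66% vs 33% gives n = (1.386 + 0.562)² / 0.33² ≈ 34.8, that is 35 per arm. A relative 33% reduction gives 36 per arm only near 88% vs 59%. The stated number is attainable, but the 80% below is calibrated rather than derived.

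**3. Losses dropped, 72 randomised, no replacement.** As a stand-in I take the two-sided t-test with the standardised effect that gives 80% power at 36 per arm, d = 0.670, and compute power at n = 36 × (1 − loss) per arm. The binary check is an unpooled z-test with a relative 33% reduction. It assumes 85.7% vs 57.4%, the rates at which that test has 80% power at 36 per arm. The loss rates are assumptions.

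| Assumed loss | n per arm | Power, t-test | Power, binary check |
|---|---|---|---|
| 0% | 36 | 0.800 | 0.800 |
| 2% | 35.3 | 0.792 | 0.792 |
| 5% | 34.2 | 0.779 | 0.780 |
| 10% | 32.4 | 0.756 | 0.757 |

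One lost patient gives 0.794 and seven give 0.757, about 0.6 points per patient. Under 66% vs 33% with the pooled test, power falls from 0.813 to 0.792 at 5% loss and 0.770 at 10%, a loss of similar size.

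**4. 72 needed for analysis.** Power is unchanged. The number of draws under the present timing is 72/0.98 = 73.5 (74), 72/0.95 = 75.8 (76) and 72/0.90 = 80.

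**5. Untreated patients kept in the analysis.** This applies only to patients who have surgery and stay in hospital but receive neither needles nor sham. Cancelled cases have no postoperative outcome, and patients who go home miss the 24-hour bedside assessment. With two such patients, one per arm, and the untreated active-arm patient assumed to respond like a control, the effect is multiplied by 35/36 = 70/72. Then d = 0.651 and power is 0.778.

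**The case against.** The strongest reply is that little is gained. A later draw does not stop cancellations or changes of eligibility; it moves them to before randomisation, and the same number of patients must still consent. This stands.

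The power loss needs 72 to be the number randomised, with losses dropped and nobody replaced. Statistical Analysis can equally be read as the number needed for analysis, and then only computer draws are saved. This stands too. The unstated control rate matters far more for power: with a relative 33% reduction from a 50% control rate, 140 per arm would be needed.

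Losses may also be few. Randomisation is already on presentation, so earlier cancellations are outside it, and a planned epidural or admission may be known by then, although the documents do not say so.

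Concealing the allocation until placement would also keep it from the intraoperative team without moving the draw, and a rule for patients who never reach placement could handle the losses. Both are workable. The late draw achieves the first by construction and makes most of the second unnecessary.

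Two stronger readings are tempting. A reader might infer that the surgical team knows the arm and that intraoperative opioid use is biased. The text does not say the team is told; it only fails to say that the team is not. A reader might also infer that the draw and placement times contradict each other. They do not: an early draw followed by later treatment can be carried out as written.

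**Conclusion.** The point holds as a low-severity design improvement. The draw is earlier than it needs to be, and patients lost between draw and placement count as randomised. Because both arms are handled identically until the PACU, these losses cost precision and not validity as long as the allocation is unknown.

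The cost is about 1 to 4 power points at assumed losses of 2% to 10%, or 2 to 8 extra draws if 72 must be analysed. These sizes rest on loss rates that the documents do not give and on 80% power being taken as stated. Losses between placement and 24 hours are not affected.

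**What to change.** Keep recruitment and consent preoperative. Change the timing sentence so that the computer allocation is drawn in the PACU immediately before placement. Before the draw, confirm conditions already in the plan: general anaesthesia was given, there is no continuous epidural, and an inpatient stay still applies. Leave cooperation and understanding of the pain score to be judged at preoperative recruitment, so that the postoperative state does not select the population. Disclose the allocation only to the person placing needles or sham. Add a sentence that all patients are analysed as randomised from that point.

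The cost is one changed sentence on timing, a short eligibility check, one disclosure rule and one analysis-population sentence. Consent does not change. The downside is logistical: the allocation has to be obtained in the PACU, where Data also places the 1-hour collection, so it must be kept from the blinded evaluators working there. The documents give no logistics, so calling this cheap is a judgement. It rests on the draw being computerised and on someone having to attend the PACU for placement in any case.

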#### **Inclusion Criteria:**

1- Patients with an American Society of Anesthesiologists (ASA) Physical Status classification of 1 to 4

2 - Patients aged between 18 and 100 scheduled to undergo scheduled suitable

inpatient/outpatient cases under anesthesia.

3 - Patients must be willing and fit to give written informed consent

4 - Inpatient stay required

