#### **Statistical Analysis:**

An unpaired students-t-test procedure (two-sample assuming equal variances, two-tail significance p<0.05, 95% confidence interval) was performed to examine mean differences between the two

study groups on all continuously scaled variables. A Repeated measures ANOVA will be used to measured differences between time for continuous variables at the 2 measured time points (1 hour and 24 hours). Assumptions of normality and/or homogeneity of variance will be checked and verified. Comparisons between study groups on proportional differences will be examined using a non-parametric Fisher's Exact Chi-square test, when applied to 2x2 tables. Statistical significance will be set at a p-value  $\leq 0.05$ . All continuous data will be expressed as the mean with 95% upper and lower confidence intervals or Mean  $\pm$  Standard deviation.

A binary outcome, superiority power analysis based on a rate of 33% reduction of opioid consumption in the auricular battlefield acupuncture group compared to controls (sham auricular battlefield acupuncture) concluded 72 participants (36 patients per group) would be necessary to achieve 80% power with a p<0.05.

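### General surgery and urology inpatients are pooled in a trial of 72 with no stratification described and unadjusted tests: the comparison is valid, but precision is given away that specialty could recover at little cost

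*Combined protocol and SAP*

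**What the plan says.** Study Design and Methods compares real with sham acupuncture "in patients undergoing general surgery and urology cases with general anesthesia". The Inclusion Criteria are broad: ASA class 1 to 4, and "Patients aged between 18 and 100 scheduled to undergo scheduled suitable" cases, with no limit on type or size of operation. They do narrow the setting, with "Inpatient stay required".

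The allocation method is given in one sentence, in the paragraph after the Exclusion Criteria: "Computerized randomization will take place at the time the patient presents for surgery". Stratification, blocking and minimisation are not mentioned anywhere.

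The Statistical Analysis section plans an equal-variance two-sample t-test for continuous variables, a repeated measures ANOVA over the 1-hour and 24-hour assessments, and Fisher's exact test for proportions. None has a term for specialty or case type. The sample size is described as "A binary outcome, superiority power analysis based on a rate of 33% reduction of opioid consumption" and "concluded 72 participants (36 patients per group) would be necessary to achieve 80% power". The list of recorded items in the Data section covers post-procedure assessments and does not name specialty or procedure.

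**The concern.** Specialty is known from the surgical schedule when the patient is randomised. If it predicts 24-hour opioid use, pain or PONV, leaving it out of both the randomisation and the analysis has two consequences.

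- **Precision.** Variation between specialties remains in the error term, so standard errors are larger than they need be and power is lower.
- **Balance.** With 36 per arm, the share of urology patients can differ noticeably between arms by chance. An unadjusted result is then harder to interpret, and readers will ask for an adjusted analysis that was not prespecified.

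What is at stake is efficiency and ease of interpretation in a small trial. The validity of the test is not in question.

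**Working it through.** **The plan's own figure.** The Statistical Analysis section gives 72 in total for 80% power at p<0.05, a binary outcome and a 33% reduction, but no control rate, and it does not say whether 33% is absolute or relative. The figure can therefore be matched only by assuming a rate. With the usual two-sided two-proportion formula, without continuity correction:

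- 65% v 32% (absolute reading) gives 34.8, so 35 per arm and 70 in total.
- 88% v 59% (relative reading, 0.88 x 0.67) gives 35.07, so 36 per arm and 72 in total.
- 70% v 47% (relative reading) gives 71 per arm.

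The Data section measures opioid use in morphine equivalents, so the illustrations below treat it as continuous and 33% as a reduction in the mean. That reading is an assumption.

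**Other assumptions** (none is in the documents): half the patients in each specialty; mean 24-hour opioid use of 30 v 15 mg (2-fold) or 22.5 v 15 mg (1.5-fold); within-specialty coefficient of variation (CV) of 0.6 to 1.0.

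**Chance imbalance, 36 per arm.** P(difference of 8 or more patients, either direction) is 0.076 with independent binomials and 0.098 with exactly 36 of 72 in each specialty (hypergeometric). 8/36 = 22 percentage points. In the hypergeometric case about 4.9% fall in each direction.

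**Shift from an 8-patient imbalance** = 8/36 x difference between specialty means.

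- 2-fold: 8/36 x 15 = 3.3 mg; 3.3/22.5 = 15% of the mean.
- 1.5-fold: 8/36 x 7.5 = 1.7 mg; 1.7/18.75 = 9% of the mean.

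**Variance explained.** Between-specialty variance B = (difference/2)². Within-specialty variance W = average of (CV x mean)² over the two specialties. R² = B/(B+W). The unadjusted N that would match the precision of 72 adjusted patients is about 72/(1-R²).

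| Means (mg) | CV | B | W | R² | 72/(1-R²) | Worth |
|---|---|---|---|---|---|---|
| 30 v 15 | 0.6 | 56.25 | 202.5 | 0.217 | 92.0 | 20 |
| 30 v 15 | 0.8 | 56.25 | 360 | 0.135 | 83.2 | 11 |
| 30 v 15 | 1.0 | 56.25 | 562.5 | 0.091 | 79.2 | 7 |
| 22.5 v 15 | 0.6 | 14.06 | 131.6 | 0.097 | 79.7 | 8 |
| 22.5 v 15 | 0.8 | 14.06 | 234 | 0.057 | 76.3 | 4 |
| 22.5 v 15 | 1.0 | 14.06 | 365.6 | 0.037 | 74.8 | 3 |

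**Power for a 33% difference in means, 36 per arm** (two-sided 0.05, SE = SD x √(2/36)).

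- 30 v 15 mg, CV 0.8: the target is 0.33 x 22.5 = 7.4 mg. Unadjusted SD is √416.25 = 20.4 and SE 4.8 mg, giving power of about 33%. Adjusted SD is √360 = 19.0 and SE 4.5 mg, giving about 37%.
- Total SD of half the mean, roughly the value at which 36 per arm gives 80% power, with a 1.5-fold difference: the SE falls from 0.118 to 0.108 of the mean, and power rises from about 79% to about 85%. This case implies less spread within specialty than the table assumes.
- Same SD with no specialty difference: about 79% either way.

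**Type I error.** In simulation (8,000 runs per setting) the unadjusted t-test rejected a true null in 4.9-5.3% of trials.

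**The case against.** The strongest reply is that randomisation already deals with chance imbalance. A reader might infer that an uneven case mix could mimic or hide much of the 33% effect, and the figures do not support that. Type I error stays near 5%. Under the 2-fold assumption with CV 0.8, an 8-patient imbalance moves the difference by 3.3 mg against a standard error of 4.8 mg, about 0.7 standard errors, and more than 90% of trials would have a smaller imbalance. By the normal approximation, a shift of at least half the 33% target has probability of about 3.7% at a 2-fold difference and 0.05% at 1.5-fold; a shift of the whole 33% has probability of about 0.003% at 2-fold. This part of the objection stands, so the point is limited to precision and interpretability.

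It is also fair that the key input is not in the documents: they give neither specialty shares nor outcomes by specialty. That specialty predicts opioid use is plausible given the breadth of eligible cases, but it is assumed.

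Two further inferences go beyond the text. The documents do not say that randomisation is unstratified; they are silent. Nor does the absence of specialty from a list of post-procedure assessments show that it will go unrecorded.

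Finally, the likely driver is size of operation, and each specialty may include small and large cases. Requiring an inpatient stay, excluding continuous epidurals and using general anaesthesia with a single intraoperative opioid also narrow the range. Specialty may therefore be a weak proxy. That limits the gain but costs almost nothing, since power is essentially unchanged when specialty is not prognostic. Adjustment alone would recover most of the precision; stratification mainly adds balance.

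**Conclusion.** The point holds as a low-cost improvement to a valid design. The plan pools two specialties in 72 patients, describes no stratification, and uses tests that leave any specialty effect in the error term. Under the stated assumptions (50:50 mix, 1.5-fold to 2-fold difference in opioid use, within-specialty CV of 0.6 to 1.0), specialty accounts for about 4-22% of the variance and adjusting is worth about 3 to 20 patients. In the two illustrations the power gain is about 4 points (33% to 37%) and 6 points (79% to 85%). The 9-15% shift applies to an imbalance reached or exceeded in about 8-10% of trials, in either direction.

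These figures show scale only. They depend on inputs that the documents do not give and on reading the 33% as a mean reduction, whereas the sample size is framed as binary. They do not show that the planned tests are biased or that a false positive is more likely than 5%.

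**What to change.** 1. **Randomisation paragraph (after Exclusion Criteria).** State the method. Stratify the computerised randomisation by specialty (general surgery or urology), using permuted blocks of varying size.
2. **Data.** Record specialty at baseline and report its balance between arms.
3. **Statistical Analysis, continuous outcomes.** An unpaired t-test cannot take a covariate. Replace it with a linear model (ANCOVA) of arm plus specialty, and include specialty as a factor in the repeated measures model.
4. **Statistical Analysis, binary outcomes.** Fisher's exact test on a single 2x2 table cannot take a covariate either. Replace it with a specialty-stratified test, for example an exact Mantel-Haenszel test.

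Steps 3 and 4 should go with step 1, because stratifying and then analysing without the stratum leaves the precision unused.

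The cost is one degree of freedom, two randomisation lists in place of one, and rewriting the named tests. The target of 72 need not change, and no patients or procedures are added. If specialty proves a weak proxy for size of operation, there will be little or no gain.

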#### **Anesthetic Plan:**

The anesthetic management will be general anesthesia with the provision of intravenous opioids intraoperatively and during recovery. Fentanyl will be the sole intra operative opioid. No other alterations of anesthetic management will take place pre or intra operatively. The battlefield acupuncture or sham battlefield acupuncture will be placed in the postoperative care unit (PACU).

#### **Acupuncture Plan**

Typically acupuncture needles which are semi-permanent needles have the characteristics of remaining in the ear acupoints for up to 3-4 days before being pushed out toward to the surface by the previous flattened epidermis. The test arm (treatment group) will received actual acupuncture needles, while the control arm will received sham or placebo acupuncture via pressing of a blunt needle on the specified BFA locations and then application of adhesive stickers. In the control group simulating acupuncture, the needles will never enter the patients' skin and will give the impression to the patient that the procedure has taken place. The ear

treated will be covered with a bandage via non-skin sensitive tape so as to blind the patient to which treatment group they are in.

### **Techniques:**

The treatment group (Group 1) will receive postoperative auricular battlefield acupuncture. The control group (Group 2) will receive sham (placebo) postoperative auricular battlefield acupuncture as described above.

### Data:

Data gathering will be performed by [name], MD and/or a CRNA. Data collection will occur in the PACU (Post-Anesthesia Care Unit) before the PACU nurses evaluate the patient for discharge. Assessment will occur at 1 hour and 24 hour post procedure. The assessment will occur on the next day by either a medical student and/or CRNA at the patients' bed side.

Assessment of the battlefield acupuncture efficacy will be performed by testing the incidence of PONV, incidence of postoperative anxiety, and pain. Pain will be assessed via the visual analog scale (VAS) scoring system.

A study investigator will record the following:

- 1. At times 1 hour and 24 hours the following will be assessed:
- 2. Incidence of PONV
- 3. Incidence of postoperative anxiety
- 4. Pain score on an 11-point (0 to 10) Visual Analog Scale (VAS) at rest and with activity
- 5. Postoperative opioid consumption via morphine equivalents used
- 6. Patient satisfaction with analgesia score (0 to 100%)

7. Any occurrence of acupuncture site infection, acupuncture site bleeding, allergic reaction to acupuncture needles, or scar tissue formation at site of acupuncture needle.

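### Opioid counting has no start tied to needle placement and no pre-needle value is recorded, so opioid given before treatment can enter the outcome

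*Combined protocol and SAP*

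**What the plan says.** The Anesthetic Plan provides general anesthesia with "provision of intravenous opioids intraoperatively and during recovery". It places the needles or sham in the PACU and gives no time after arrival. The Data section lists the opioid outcome as "Postoperative opioid consumption via morphine equivalents used", one of several items taken at 1 and 24 hours. On timing it says "Assessment will occur at 1 hour and 24 hour post procedure". Neither section says when opioid counting begins, asks for the time of placement, or lists a pain, nausea, anxiety or opioid value before it.

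On allocation, the text after the exclusion criteria says "Computerized randomization will take place at the time the patient presents for surgery". On blinding, Study Design and Methods says "Both the evaluators for post procedure assessment along with the patient will be blinded" and does not mention the staff who give opioids.

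Statistical Analysis compares continuous outcomes with an unadjusted two-sample t-test, adds a repeated measures ANOVA over the two follow-up times, and uses Fisher's exact test for proportions. No covariate is named.

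**The concern.** Treatment starts after surgery, in a unit where opioid is already being given. A data collector at 24 hours could total opioid from the end of surgery, from PACU arrival or from placement, and each total would comply with the text. The first two can include opioid that the treatment cannot affect. Opioid consumption is also the quantity on which the trial is sized.

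Two further matters follow from the same timing. A score taken just before placement would be a natural covariate in a mixed population (general surgery and urology, ASA 1 to 4, age 18 to 100), and it cannot be recovered later if it is not taken. Also, allocation exists from before surgery, so balance between arms up to placement depends on the people giving care not knowing it.

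**Working it through.** **1. Order of events.** Randomisation on presentation for surgery; operation with intraoperative opioid; PACU with further intravenous opioid; needle or sham at an unstated time in the PACU; assessments at 1 and 24 hours. The interval from PACU arrival to placement, and the opioid given in it, are stated nowhere. Both must be assumed.

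**2. The plan's own figure.** Statistical Analysis gives 36 per group and 80% power for a binary outcome and a 33% reduction. No control rate is given, so the figure cannot be reproduced from the stated inputs. With a two-sided pooled test and no continuity correction, an absolute fall of 33 points needs 34 to 35 per arm for control rates of 60% to 75%. A relative fall of 33% needs 36 per arm near a control rate of 88%, and 140 at 50%. Read as a mean amount, 33% needs 37 per arm at a coefficient of variation (CV) of 0.50. The figure is under-specified, not shown to be wrong. Below, 36 per arm and 80% power are taken as assumptions for a continuous outcome.

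**3. Relative reduction.** Set the control mean after placement to 1 and the treated mean to 0.67. Let pre-needle opioid add m to both arms. The absolute difference stays (1 + m) − (0.67 + m) = 0.33. The relative reduction becomes 0.33/(1 + m):
- m = 0.10: 0.33/1.10 = 30%
- m = 0.25: 0.33/1.25 = 26%
- m = 0.50: 0.33/1.50 = 22%

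**4. Power of the t-test on the total.** With 36 per arm, 70 degrees of freedom and two-sided 0.05, a standardised difference d = 0.6696 gives 80% power (noncentral t, noncentrality d·√18 = 2.84). With equal CV in both parts, the pre-needle SD is m times the post-needle SD. At correlation ρ the variance is multiplied by V = 1 + m² + 2ρm, and power is taken at d/√V.

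| m | V, ρ = 0 | Power | V, ρ = 0.3 | Power |
|---|---|---|---|---|
| 0.10 | 1.010 | 79.6% | 1.070 | 77.3% |
| 0.25 | 1.0625 | 77.6% | 1.2125 | 72.1% |
| 0.50 | 1.250 | 70.7% | 1.550 | 61.4% |

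A negative correlation can remove the loss. At ρ = −0.2 and m = 0.10, V = 1 + 0.01 − 0.04 = 0.97, slightly below 1. Added noise is therefore usual, not certain.

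**5. Adjustment.** If the covariates have joint correlation r with the outcome, power is taken at d/√(1 − r²). Three covariates leave 72 − 2 − 3 = 67 degrees of freedom.

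| r | 1 − r² | Power |
|---|---|---|
| 0 | 1.00 | 79.95% |
| 0.1 | 0.99 | 80.3% |
| 0.2 | 0.96 | 81.5% |
| 0.3 | 0.91 | 83.5% |
| 0.5 | 0.75 | 89.8% |

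The gain is under 2 points at r of 0.2 or less. Adjusting for useless covariates costs under 0.1 point.

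**6. PONV and anxiety.** The Data section says "Assessment of the battlefield acupuncture efficacy will be performed by testing the incidence of PONV", with anxiety and pain alongside, and does not say whether incidence is cumulative or is status at each time. If it is cumulative, a share f already has the event before placement, and later risk is otherwise equal, the risk difference becomes (1 − f)(p₁ − p₂). If it is status at 1 and 24 hours, this dilution does not arise.

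**The case against.** The strongest reply is that *post procedure* already sets the clock. The Acupuncture Plan uses the word for the acupuncture itself, saying that the sham "will give the impression to the patient that the procedure has taken place", so consumption at 1 and 24 hours would naturally mean use since then. That is the most natural reading of the assessment times, and it narrows the ambiguity. It still fixes when the patient is assessed, not when opioid starts to accrue, and the outcome itself is labelled postoperative.

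The rest of the reply concerns size and status, and most of it stands. The 80% is borrowed from a binary calculation, so the power figures are illustrations and not the power of this plan. ANCOVA is an improvement on a valid test, with a gain that may be small. The PONV and anxiety effect depends on an unsettled reading.

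A reader might infer larger losses by letting pre-needle opioid add 10%, 25% or 50% to the variance instead of the mean: 76%, 71% or 63% power at correlation 0. Those are different scenarios from the dilution in step 3. With equal CV, 50% extra variance needs a pre-needle mean of √0.5, or about 71% of the later mean, and nothing in the documents points to that.

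A reader might also infer that the comparison is biased. Randomisation balances pre-needle opioid in expectation unless knowledge of allocation changes earlier care, and the documents do not show that it does. The Anesthetic Plan says that anesthetic management before and during surgery is otherwise unaltered. This limits the concern about intraoperative care, but it does not cover opioid given in the PACU before placement.

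**Conclusion.** The point holds as a gap in definition and a missed, cheap gain in precision. The opioid outcome can include use that treatment cannot affect. In expectation this leaves the absolute difference intact, reduces the relative one and usually adds noise. On the assumptions in step 4, the cost ranges from almost nothing to about 19 points of power (80% to 61%). The documents give neither the time to placement nor the pre-needle amount, so the true cost is unknown, and it is negligible if placement follows PACU arrival at once. The documents do not support calling the t-test invalid or the comparison biased. Pain scores are affected only through the missing pre-needle value.

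**What to change.** In Data, state: *Time zero is needle or sham placement, time-stamped. Pain, nausea and anxiety are recorded just before it. Assessments are 1 and 24 hours after it. The main opioid outcome is morphine equivalents from time zero; total postoperative opioid is secondary.* State also whether PONV and anxiety are new events after time zero or status at 1 and 24 hours.

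In Statistical Analysis, replace the unadjusted t-test with ANCOVA on pre-needle pain, opioid given before placement (from existing records) and service (general surgery or urology). Keep Fisher's test for binary outcomes.

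Two of these covariates are measured after randomisation, so they are safe only if allocation could not have influenced them. Reveal allocation only at placement, once the pre-needle values are recorded. If that is not possible, adjust only for service and other variables fixed before randomisation.

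The cost is one bedside score of about a minute, one time stamp, holding allocation back, and revised wording; no extra patients are needed. The main opioid estimate is then limited to use after placement, which is why the total is kept as secondary. The covariate gain may be small.
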